8. STATISTICAL PLAN

8.1. Sample Size Determination

Using combined results from selected Phase 1 studies on oritavancin pharmacokinetics with the approved formulation, the observed CV of AUC_{0-72} and AUC_{0-168} were 25.4% and 26.3%, respectively. Using a slightly larger CV value of 30% to be conservative, the table below shows estimated power values in a parallel study design to demonstrate equivalence of AUC of the new formulation (test, T) relative to the approved formulation (reference, R), assuming various true T/R ratios of geometric means of AUC_{0-72} and AUC_{0-168} . The table uses a sample size of 100 subjects randomized in 1:1 ratio to the test and reference groups and uses the standard 80% to 125% equivalence limits. A study design of 50 subjects in each of the test and reference groups should have $\geq \sim 90\%$ power to demonstrate AUC equivalence, if the true T/R ratios are within 0.95 to 1.05.

True T/R Ratio	Power
0.95	89.5%
1.0	96.7%
1.05	90.2%

8.2. Randomization

With a sample size of approximately 100, subjects will be randomized in 1:1 ratio in a parallel fashion to the test (new formulation) and reference (approved formulation) groups.

8.3. Analysis Population

8.3.1. Intent-to-Treat (ITT) Population

All subjects randomized will be analyzed according to the treatment arm to which they were randomized. Subject disposition, demographic, and baseline characteristics will be summarized by treatment using the ITT population

8.3.2. Pharmacokinetics (PK) Population

All subjects who have received the full dose of oritavancin and have one valid sample measured for study drug levels. The PK population will be the primary population for the PK analysis.

8.3.3. Safety Population

All subjects who have received any amount of IV oritavancin will be included in the safety population. Treatment group will use it as actually received. The safety population will be the primary population for all the safety analyses.

8.4. General Statistical Considerations and Definitions

8.4.1. Software

All data listings, summaries and statistical analyses will be generated using SAS® Version 9.4 or above, or equivalent statistical software. PK analysis (including the calculation of PK parameters such as AUC, C_{max}, T_{1/2}, etc.) will use WinNonlin or relevant software, and will be performed by PK vendor.

8.4.2. General Statistical Methods

All study-collected data will be summarized by treatment group using descriptive statistics, graphs, and/or raw data listings. Unless otherwise specified, descriptive statistics for continuous variables will include number of subjects (n), mean, standard deviation (SD), median, quartiles (Q1 and Q3), minimum (min) and maximum (max) values. Analysis of categorical variables will include frequency and percentage. For the summary by visit analysis, graphic display using box-whisker or mean +/- standard error plot will be generated.

8.4.3. Analysis Windows and Baseline

All data collected in the study will be included in the analysis. Unless otherwise specified, the last evaluation prior to the initiation of study drug will be considered the "Baseline" evaluation for analysis. For microbiologic assessments, any pathogen identified from within 72 hours prior to screening up to and including Day 2 will be considered as baseline.

8.4.4. Missing Data Handling

Unless otherwise specified, missing data will not be imputed and will be excluded from the associated analysis.

Partial dates: Dates missing the day of the month, or both the day and month of the year will adhere to the following conventions:

- The missing day of onset of an adverse event or start date of a concomitant medications will conservatively be set to the earlier of:
 - first day of the month that the event occurred, as long as it is after the date of the start of first treatment
 - one day after the first dose, if this is the same month that the event occurred
- The missing day of resolution of an adverse event or end date of a concomitant medications will be set to the last day of the month of the occurrence.
- If the onset date of an adverse event or start date of a concurrent therapy is missing both the day and month, the onset date will be set to the earliest of:
 - January 1 of the year of onset, as long as it is after the first dose
 - one day after the first treatment, if this is the same year that the event occurred

- If the resolution date of an adverse event or end date of a concomitant medications is missing both the day and month, the date will be set to:
 - December 31 of the year of occurrence, if the patient is continuing treatment
 - The date of patient discontinuation, if the event is not ongoing

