8.3.2. Prohibited Medications

As the safety data collection in this trial is extremely important, use of additional antibiotics during the study period should be minimized unless the patient is a treatment failure requiring unexpected rescue antibiotics or requires additional antibiotics to treat a new infection during the study.

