14.4.2. Study Drug and Concomitant Medications

Summary of each prior (pre-baseline) medication and concomitant (baseline or later) medication will be provided by treatment for the safety population. Medication will be coded with World Health Organization (WHO) Drug Dictionary Enhanced. Subjects will be counted only once by medication.

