8.5.5.1. Adverse Events

The MedDRA Version 22.0³ or later will be used for coding AEs. Adverse events (AEs) will be graded using the 5-point Common Terminology Criteria for Adverse Events (CTCAE) criteria (Version 5)¹. An AE (classified by preferred term) occurring from the start of study drug will be counted as treatment emergent AE (TEAE) either if it was not present at baseline or if it was present at baseline but increased in severity during the period of observation.

An overall summary of subjects reporting a TEAE in each treatment group will be provided for the Safety population. This analysis will include: the number and percentage of subjects reporting any TEAE, any TEAE presented by maximum severity, any TEAE related to study drug, any SAE, any SAE related to study drug, any SAE leading to premature discontinuation of study drug, any SAE with an outcome of death, any TEAE leading to study discontinuation, any TEAE leading to study drug discontinuation or interruption, and any TEAE of special interest will be summarized for the Safety population.

The number and (percentage) of subjects reporting TEAEs for each preferred term will be tabulated by system-organ class, by system-organ class and severity, and by system-organ class and relationship to study drug. A summary of TEAEs occurring in $\geq 5\%$ (or ≥ 2 subjects) of either formulation group (based on MedDRA preferred term) sorted by decreasing frequency in the new formulation arm will also be provided. Likewise, the number and percentage of subjects reporting a serious TEAE and reporting a study-drug related SAE in each treatment group will be tabulated separately by system organ class and preferred term. Likewise, summaries of TEAEs leading to study discontinuation or study drug discontinuation or interruption will also be provided by system organ class and preferred term. For all analyses of TEAEs if the same event (based on preferred term) occurred for the same subject more than once, the subject will be counted only once for that preferred term using the most severe or related occurrence for the summary by severity, or relationship to study drug, respectively.

A listing of all serious TEAEs will be provided and will include subject ID, study day(s) of event, duration of study drug administered prior to onset (minutes), system organ class, preferred term, verbatim term, severity, relationship to study drug, action taken with study drug, and outcome.

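### SAP 8.4.4 dates every AE onset or medication start with a missing day in the dosing month (or missing day and month in the dosing year) to the day after dosing, so an infusion-day event with a partial date is always listed as Day 2

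*SAP*

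**What the plan says.** SAP 8.4.4 (Missing Data Handling) begins by leaving missing data unimputed and out of the associated analysis unless otherwise specified. It then specifies rules for partial dates.

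- **Day missing, onset or start.** "The missing day of onset of an adverse event or start date of a concomitant medications will conservatively be set to the earlier of" two candidates: (a) "first day of the month that the event occurred, as long as it is after the date of the start of first treatment"; (b) "one day after the first dose, if this is the same month that the event occurred".
- **Day and month missing, onset or start.** The earliest of January 1 of the known year, provided it is after first dose, or "one day after the first treatment, if this is the same year that the event occurred".
- **Day missing, resolution or end.** The date "will be set to the last day of the month of the occurrence".
- **Day and month missing, resolution or end.** December 31 if the patient is still on treatment, or the patient's discontinuation date if the event is not ongoing.

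Three other places use these dates. SAP 8.5.5.1 plans listings of serious TEAEs, and of TEAEs leading to discontinuation or interruption, that show "study day(s) of event, duration of study drug administered prior to onset (minutes". Protocol 14.4.2 divides medications by timing: "Summary of each prior (pre-baseline) medication and concomitant (baseline or later) medication will be provided by treatment for the safety population". SAP 8.5.3 asks for the two medication summaries separately but gives no rule for assigning a drug to one or the other.

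**The concern.** The trial compares a 1-hour with a 3-hour infusion of a single dose, and Protocol 5.4.1.3 notes that a shorter infusion may raise Cmax and bring adverse events with it. Day 1 is therefore the day on which AE timing matters most, yet the imputation rule cannot return Day 1. A Day 2 onset also implies that the whole infusion was given before the event began, which contradicts an event that started during the infusion or interrupted it.

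The same rule covers medication starts. Protocol 8.3 collects treatments received from 14 days before dosing, so pre-dose starts are expected in the data, but no branch of the rule can return a pre-dose date. What is at stake is the accuracy of onset days in the safety listings and, possibly, the split between prior and concomitant medication.

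**Working it through.** The plan gives no figure to reproduce here. The check applies the written rule literally, reading after as strictly later.

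**Inputs.** The candidates and end-date rules are those of SAP 8.4.4. The infusion day is Day 1 (Protocol 10.5), so dose date + 1 is Day 2. AEs are assessed from study drug administration to Day 15 (SAP Table 1, note 8). Medications are collected from 14 days before dose (Protocol 8.3). Assumption: all 365 dosing dates of a non-leap year, and all start lags of 1 to 14 days, are equally likely.

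**1. Why only one branch works.** Let dosing fall on day d of its month, d ≥ 1. Candidate (a) needs day 1 of that month to be later than day d, that is 1 > d, which is impossible. Candidate (b) always applies in the dosing month, so the result is dose date + 1. Likewise January 1 of the dosing year can never be later than a dose given in that year.

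**2. Infusion-day AE.**
- Day missing: Day 2 for 365/365 dosing dates; candidate (a) qualifies for 0/365.
- Day and month missing: Day 2 for 365/365.

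**3. Direction of error over the AE period.** Take onsets on Days 1 to 15 with the month known and the day missing: 365 × 15 = 5,475 combinations. The imputed date is earlier than the truth in 4,589, exact in 521 and later in 365. All 365 late results are the Day 1 onsets. The rule errs early or is exact everywhere except on the infusion day.

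**4. Order of onset and resolution.** If dosing is on the last day of a month (12/365 = 3.3% of dates), dose date + 1 lies in the next month, outside the known month. A resolution in the known month with its day missing is set to the last day of that month, which is then one day before the imputed onset. Separately, for any dosing date, an infusion-day AE with a missing onset day and a complete Day 1 resolution date is given an onset after its resolution.

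**5. Medication started 1 to 14 days before dose, day missing.** The start shares the dosing month when d − 1 ≥ lag.
- Dosing days 1 to 14 of a month contribute 0 + 1 + … + 13 = 91 same-month starts; each later day contributes 14.
- Over the year: 12 × 91 + 14 × (365 − 12 × 14) = 1,092 + 2,758 = 3,850 of 365 × 14 = 5,110, or 75.3%, set to Day 2.
- The other 12 × 105 = 1,260 (24.7%) began in an earlier month. Neither branch applies, so they get no date.
- Pre-dose date returned: 0.

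**6. Same starts, day and month missing.** Only dosing on January 1 to 14 can put the start in the previous year: 14 + 13 + … + 1 = 105 cases (2.1%) with no date. The other 5,005 (97.9%) become Day 2. Pre-dose date returned: 0.

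**7. With the dose date as floor for AE onset.** An infusion-day AE with a partial date is dated Day 1 for 365/365 dosing dates, against 0/365 now.

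**The case against.** The strongest reply is that little in the results depends on this. Much of it stands.

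- **TEAE tables.** A reader might infer that the safety tables are wrong. They are not: Day 1 and Day 2 onsets are both treatment-emergent under SAP 8.5.5.1, and no time-to-onset table is planned. The AE effect is confined to onset day and minutes of drug before onset in listings.
- **Frequency.** Infusion-day events are recorded as they occur (Protocol 10.5), SAEs are reported within 24 hours of awareness (Protocol 13.4.1), and an event that stops the infusion is tied to the dosing record. Such events are the least likely to lack a day. The documents give no count of partial dates.
- **Prior/concomitant tables.** A reader might infer that these come out wrong. That follows only if the imputed start date decides the category. The timing split in Protocol 14.4.2 makes this plausible, but SAP 8.5.3 does not say so, and medications are recorded separately at screening, pre-dose and later visits (Protocol 10.2, 10.4, 10.6 to 10.9).
- **Scope.** SAP 8.4.4 names concomitant medications and concurrent therapy. Protocol 8.3 uses the first term loosely enough to include pre-dose drugs, but it is not certain that the rule was meant for every prior medication. Long-standing drugs mostly began in an earlier month or year, so they would go undated, not be re-dated to Day 2.
- **The 75.3%.** This describes how the rule treats a drug begun in the last 14 days with only its day unknown. Protocol 8.3 collects drugs received, not begun, in that window, so the figure does not measure impact on the trial.
- **Rescue treatment.** A reader might infer that a pre-study antibiotic re-dated to Day 2 would be analysed as rescue. Protocol 8.3.2 limits extra antibiotics "unless the patient is a treatment failure requiring unexpected rescue antibiotics" or has a new infection, but that guides conduct; the SAP plans no rescue or efficacy analysis.

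None of this answers the central point: followed as written, the rule cannot give the right date for an infusion-day AE or a pre-dose start.

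**Conclusion.** The concern holds as a minor defect in a stated rule. For partial dates in the dosing month or year, SAP 8.4.4 always returns Day 2. For an infusion-day AE that is one day late on every possible dosing date, contrary to the rule's own description as conservative, and on 12 of 365 dosing dates the imputed onset falls outside the known month and can follow the imputed resolution. Pre-dose medication starts are dated after dosing or left undated, never dated before dosing.

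TEAE incidence, severity and relationship summaries are unaffected. An effect on the prior/concomitant tables depends on an unstated classification rule. The number of affected records is unknown and may be small. The medication percentages rest on uniform dosing dates and start lags; the result for infusion-day AEs holds for every dosing date and needs no such assumption.

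**What to change.** Amend SAP 8.4.4, with a matching sentence in 8.5.3:

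1. **AE onset.** Impute the later of the first day of the known period and the date of first dose (Day 1), and never a date after a known resolution date.
2. **Medications.** Allow pre-dose imputed dates. Decide prior versus concomitant from the visit at which the drug was recorded (screening or pre-dose versus post-dose) and any known end date. Use the first of the month or January 1 only when the record does not show a post-dose start.
3. **End dates.** Replace the branch that depends on continuing treatment, which does not fit a single infusion; the alternative, a discontinuation date, does not exist for a subject who completes the study. Use the earlier of the end of the known period and the last contact or follow-up date. Capping at the Day 15 visit instead would be wrong, because SAEs are followed beyond it (Protocol 10.9, 13.4.1).

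The cost is a few lines of text and programming. The downside is small: a post-dose medication with a partial date could be dated pre-dose if the visit record is unclear, and a same-month AE that truly began on Day 2 would be dated one day early, which is the direction the SAP says it prefers.

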8.5. Statistical Analyses

8.5.1. Subject Disposition

A disposition table will summarize the number of patients screened, randomized, treated, discontinued from study treatment and reasons for discontinuation from study and study drug by treatment groups. The table will define the ITT, PK, and Safety Populations. Indicator variables (Yes/No) will be presented in listings to identify the population flag. The reason for discontinuation from study and study drug will be summarized using the categories specified in the case report form (CRF), by treatment group.

8.5.2. Demographic and Baseline Characteristics

Subject demographics and baseline characteristics will be summarized by treatment groups using the ITT population. Unless the PK, and Safety population is significantly different from the ITT population (> 5% in total number of patients), the demographic and baseline characteristics table will not be duplicated.

Demographic and baseline variables will include:

- Age
- Sex
- Race
- Ethnicity
- Height
- Weight
- BMI
- ABSSI Disease Status

Baseline pathogens and medical/surgical history will also be summarized.

8.5.3. Prior and Concomitant Medications

Summary of each prior medication, and concomitant medication will be provided by treatment group separately for the safety population. Medication will be coded with World Health Organization Drug Dictionary Enhanced (WHODrug March 1, 2019)² and summarized using ATC Level 4 and generic drug names. Subjects will be counted only once within each period by medication.

8.5.4. Study Drug Exposure

Extent of exposure including dose amount and duration of treatment (minutes) will be summarized for the Safety population. The number and percentage of subjects who completed treatment, and who experienced dose interruptions and discontinuations will be summarized for the Safety population.

All study drug administration data will be presented in a listing.

8.5.5. Safety Analysis

Safety will be assessed according to adverse clinical events, clinical laboratory evaluations (including Coombs anti-globulin tests and oritavancin antibody assay, as applicable), and vital signs. For each safety parameter, the last assessment made prior to the first dose of study drug will be used as the baseline value for all analyses.

8.5.5.1. Adverse Events

The MedDRA Version 22.0³ or later will be used for coding AEs. Adverse events (AEs) will be graded using the 5-point Common Terminology Criteria for Adverse Events (CTCAE) criteria (Version 5)¹. An AE (classified by preferred term) occurring from the start of study drug will be counted as treatment emergent AE (TEAE) either if it was not present at baseline or if it was present at baseline but increased in severity during the period of observation.

An overall summary of subjects reporting a TEAE in each treatment group will be provided for the Safety population. This analysis will include: the number and percentage of subjects reporting any TEAE, any TEAE presented by maximum severity, any TEAE related to study drug, any SAE, any SAE related to study drug, any SAE leading to premature discontinuation of study drug, any SAE with an outcome of death, any TEAE leading to study discontinuation, any TEAE leading to study drug discontinuation or interruption, and any TEAE of special interest will be summarized for the Safety population.

The number and (percentage) of subjects reporting TEAEs for each preferred term will be tabulated by system-organ class, by system-organ class and severity, and by system-organ class and relationship to study drug. A summary of TEAEs occurring in $\geq 5\%$ (or ≥ 2 subjects) of either formulation group (based on MedDRA preferred term) sorted by decreasing frequency in the new formulation arm will also be provided. Likewise, the number and percentage of subjects reporting a serious TEAE and reporting a study-drug related SAE in each treatment group will be tabulated separately by system organ class and preferred term. Likewise, summaries of TEAEs leading to study discontinuation or study drug discontinuation or interruption will also be provided by system organ class and preferred term. For all analyses of TEAEs if the same event (based on preferred term) occurred for the same subject more than once, the subject will be counted only once for that preferred term using the most severe or related occurrence for the summary by severity, or relationship to study drug, respectively.

A listing of all serious TEAEs will be provided and will include subject ID, study day(s) of event, duration of study drug administered prior to onset (minutes), system organ class, preferred term, verbatim term, severity, relationship to study drug, action taken with study drug, and outcome.

A listing of all TEAEs leading to study discontinuation, and all TEAEs leading to study drug discontinuation or interruption and will include subject ID, study day(s) of event, duration of study drug administered prior to onset (minutes), system organ class, preferred term, verbatim term, severity, relationship to study drug, action taken with study drug, and outcome.

8.5.5.2. Laboratory Tests

Laboratory values presented will include: serum chemistry, hematology, direct/indirect Coombs test, and oritavancin antibody assay. Descriptive statistics (number of subjects with a reported value, mean, SD, median, minimum, and maximum) will be presented for quantitative laboratory parameters. Laboratory data will be summarized by visit using descriptive statistics (including absolute values and change from baseline). For qualitative laboratory parameters, tables will display the number of subjects with a reported value and percentage in each category. Laboratory results will be classified as low (L), normal (N), or high (H) according to the laboratory-supplied reference ranges from the local laboratories.

There will be separate data listings for each category of laboratory test results. Subjects with values above or below the reference range, regardless of clinical significance, will be identified in the data listings with flags for high and low values. Potentially clinically significant (PCS) values will be flagged in the listings of chemistry and hematology data.

8.5.5.3. Chemistry and Hematology Laboratory Parameters,

Laboratory values descriptive statistics will be summarized by treatment group, including absolute value and changes from baseline at each scheduled time point. Graphic display of change over time using box-whisker plot or mean +/- standard error by visit will be generated. A shift table from baseline to overall worst post-baseline (which will include values from unscheduled post-baseline visits) by category (low, normal, high) will be generated. Subjects with missing data for a given visit will not contribute to the summary statistics for that visit. Tables showing shift from baseline will also be presented.

Analyses will also be performed for each lab parameter by treatment group for incidence rates of PCS values abnormalities for subjects without a PCS value at baseline. PCS values are defined in [Table 3](#). Listings of subjects with treatment-emergent PCS (Grade 3 and 4) post-baseline laboratory abnormalities will be provided.

Table 3: Criteria for Potentially Clinically Significant Abnormal Lab Tests

Parameter	Lower limit	Upper limit
Hematology		
Red Blood Cell Count	$\leq 0.75 \times \text{LLN}$	$\geq 1.25 \times \text{ULN}$
WBC's Count	$< 2.0 \times 10^9/\text{L}$	
Neutrophil Count	$< 1.0 \times 10^9/\text{L}$	
Lymphocyte count	$< 0.5 \times 10^9/\text{L}$	
Hematocrit	$\leq 0.75 \times \text{LLN}$	$\geq 1.25 \times \text{ULN}$
Hemoglobin	$\leq 11.5 \text{ g/dL}$ Male $\leq 9.5 \text{ g/dL}$ Female	$\geq 18.0 \text{ g/dL}$ Male $\geq 16.0 \text{ g/dL}$ Female
Platelet count	$\leq 75 \times 10^9/\text{L}$	$\geq 700 \times 10^9/\text{L}$
Absolute Reticulocyte Count ¹		$> \text{ULN}$
Serum Chemistry		
BUN		$\geq 10.7 \text{ mmol/L}$
Calcium	$\leq 7.0 \text{ mg/dL}$	$\geq 15.5 \text{ mg/dL}$
CPK		$\geq 3 \times \text{ULN}$
Creatinine		$\geq 2.0 \text{ mg/dL}$
Glucose	$\leq 50 \text{ mg/dL}$	$\geq 180 \text{ mg/dL}$
Haptoglobin	$< \text{LLN}$ or decrease of 50% from Baseline	
Potassium	$\leq 3.0 \text{ mmol/L}$	$\geq 5.5 \text{ mmol/L}$
Sodium	$\leq 125 \text{ mmol/L}$	$\geq 150 \text{ mmol/L}$
Liver Function Tests (LFTs):		
Alanine Transaminase (ALT/SGPT)		$\geq 3\times, 5\times, 10\times \text{ and } 20\times \text{ULN}$
Aspartate Transaminase (AST/SGOT)		$\geq 3\times, 5\times, 10\times \text{ and } 20\times \text{ULN}$
ALT or AST		$\geq 3\times, 5\times, 10\times, \text{ or } 20\times \text{ULN}$
Total bilirubin		$\geq 1.5\times \text{ and } 2\times \text{ULN}$
Alkaline Phosphatase (ALP)		$\geq 1.5\times \text{ and } 3\times \text{ULN}$
ALT/AST $\geq 3 \times \text{ULN}$ and Total bilirubin $\geq 2 \times \text{ULN}$		
Potential Hy's Law cases:	ALT or AST $\geq 3 \times \text{ULN}$, Total bilirubin $\geq 2 \times \text{ULN}$, and ALP $\leq 2 \times \text{ULN}$	

¹. If reticulocytes are reported in % by local laboratory, these results will be converted to absolute count in the unit of 1000/mcl for this analysis.

